2. SCHEDULE OF ACTIVITIES (SOA)

2.1. Part A General Schedule of Activities

	Screening (up to 35 Days prior to Day 1)							nent Pe ay 1	eriod 1	-3			Day 2	Day 3	Treatme	Follow-up 1 (7-14 days post-last dose)	Follow-up 2 (5 dose ±	Notes
Procedure	to 35 Days pr ay 1)	Day -1	Pre-dose	4 O	15 m	30 mins	1 h	2 h	4 h	h 9	8 h	12 h	y 2 24 h	y 3 48 h	Treatment Period 4	-14 days post lose)	5 weeks after last ± 3 days)	The 2nd follow up visit is only required for those participants where challenges are
Conser	ior to		lose		mins	lins						5	5	5		last	last	being administered and blisters induced i.e. treatment period 4
General																		
Informed consent	Х																	
Inclusion and exclusion criteria	x	x													See separate Period 4 Schedule			Day -1 assessment is to recheck eligibility against medical conditions, prior therapy etc, but not against Day -1 clinical chemistry and haematology results (see Section 9.4.7).
Demography	Х														Perio			
Medical/medication/drug/ alcohol history	x	х													d 4 Schedul			Includes substance usage and family history of premature cardiovascular (CV) disease and current medical conditions.
Admission to unit for in-patient stay		Х													e of /			
Discharge from Unit following in- patient stay														х	of Activities			
Outpatient visit	х															х	х	

CONFIDENTIAL

	Screening (L						Treatm	nent Pe	eriod 1	-3					Treat	Follow-up 1	Follow-up 2 (dose	Notes
Procedure	up to 35 Day 1)						Da	ay 1					Day 2	Day 3	Treatment Period 4	(7-14 d dose)	+ 25	
	Screening (up to 35 Days prior to Day 1)	Day -1	Pre-dose	0 h	15 mins	30 mins	1 h	2 h	4 h	6 h	8 h	12 h	24 h	48 h	ariod 4	Follow-up 1 (7-14 days post-last dose)	5 weeks after last 3 days)	The 2nd follow up visit is only required for those participants where challenges are being administered and blisters induced i.e. treatment period 4
Safety Assessments including labor	atory tes	sts																
Full Physical Exam	Х																	
Brief Physical Exam		Х												Х		Х		
Vital Signs	x	x	x					x	x		x	x	x	x	Se	x	x	Blood pressure (BP), heart rate (HR), temperature, respiratory rate. See Section 9.4.4 for details on triplicate and single measurement timepoints.
12-Lead ECGs	x	x	x					x	x		x	x	x	x	See separate Period 4 Schedule of Activities	x		12 Lead ECGs will be performed in triplicate at screening, Day-1, Day 1 pre- dose, Day 2 and Day 3. Single ECGs will be performed at other time points and if any cardiac symptoms are experienced. ECGs to be performed prior to blood draws and dosing where these fall at the same nominal time.
Telemetry			<==										===>		dule			from 1 h pre-dose to 24 h post-dose
Holter monitoring (24 hours)	Х														of Activ			If a participant is rescreened the Holter will not need to be repeated.
HIV, Hep B, Hep C	Х														ities			
Haematology	х	х									х		x	x		x		Fasted screening samples. 24 and 48 hour samples will be taken prior to participants receiving breakfast
Coagulation	х										х		x	x		х		Fasted screening samples. 24 and 48 hour samples will be taken prior to participants receiving breakfast

CONFIDENTIAL

Procedure	Screening (up to 35 Days prior to Day 1)					-	Treatm Da	ient Pe ay 1	eriod 1	-3			Day 2	Day 3	Treatment Period 4	Follow-up 1 (7-14 days post-last dose)	Follow-up 2 (5 we dose ± 3 c	Notes
	Days prior to	Day -1	Pre-dose	0 h	15 mins	30 mins	1 h	2 h	4 h	6 h	4 8	12 h	24 h	48 h	eriod 4	lays post-last	5 weeks after last ⊦ 3 days)	The 2nd follow up visit is only required for those participants where challenges are being administered and blisters induced i.e. treatment period 4
Clinical Chemistry	х	х									х		x	Х		х		Fasted screening samples. 24 and 48 hour samples will be taken prior to participants
Urinalysis	х	х									х		x	х		х		Fasted screening samples. 24 and 48 hour samples will be taken prior to participants receiving breakfast
Drug / Alcohol Test	Х	Х																
Urine Cotinine	Х	Х																
Visual forearm check (cosmetic assessment or blister healing where appropriate)	X	Х														X	X	 Visual forearm checks are only required if participant is scheduled to take part in treatment period 4. Details of checks: Screening check prior to first treatment period (cosmetic assessment) Day -1 check in treatment Period 3 only. Between Day -1 and Day 2 (ie 48 hour window) (cosmetic assessment) Period 4 (cosmetic assessment) Period 4 (cosmetic assessment and blister healing). For further detail on time points in Period 4 see Section 2.1.1. Follow-up visits 1 and 2 (blister healing)

CONFIDENTIAL

Procedure	Screening (up to 35 Day 1)							nent Pe ay 1	eriod 1	-3			Day 2	Day 3	Treatment Period	Follow-up 1 (7-14 c dose)	Follow-up 2 (5 we dose ± 3 c	Notes
	Days prior to	Day -1	Pre-dose	0 h	15 mins	30 mins	1 h	2 h	4 h	6 h	8 h	12 h	24 h	48 h	4	(7-14 days post-last dose)	weeks after last 3 days)	The 2nd follow up visit is only required for those participants where challenges are being administered and blisters induced i.e. treatment period 4
AE / SAE review	SAE	s colleo	cted fro	om sigr								llow up w up vi		AEs co	llecte	d continu	uously	
Concomitant Medication Review				Mor	nitored	from fi	rst dos	e until	the en	d of th	e final	treatm	ent Pe	riod				
Treatment Administration																		
Study Drug / Placebo Administration				x											See Period 4 SoA			

CONFIDENTIAL

	Screening (-	Treatm	nent Pe	eriod 1	-3					Trea	Follow-up 1	Follow-up 2 dose	Notes
Procedure	up to 35 Day 1)						Da	ay 1					Day 2	Day 3	Treatment Period 4	l (7-14 da dose)	$+ \widehat{a}$	
	Screening (up to 35 Days prior to Day 1)	Day -1	Pre-dose	0 h	15 mins	30 mins	1 h	2 h	4 h	6 h	8 h	12 h	24 h	48 h	riod 4	Follow-up 1 (7-14 days post-last dose)	5 weeks after last :3 days)	The 2nd follow up visit is only required for those participants where challenges are being administered and blisters induced i.e. treatment period 4
Pharmacokinetics, Pharmacodynam	ics and (Geneti	cs Sai	mples														
Blood sampling for systemic PK [S1] and [S2]			Х		Х	X	Х	X	X	X	Х	X	Х	Х				
Blood sampling for intracellular PK [S3]							Х		Х		Х		Х	Х				
Blood sample for ex vivo PD assay [S4]		x	х				х		х		х	x	х	х	See separate			Six samples (3 LPS and 3 null) are required on Day -1: to be taken (LPS and null) at approximately 13:00, 17:00 and 20:00. Day 1: Two pre-dose samples (LPS and null) to be taken at approximately 08:00.
Blood sample for circulating proteins [E1a]			Х					Х	Х		Х		Х		Period 4 Schedule of Activities			
Blood sample for gene panel [E1b]			Х					Х	X		Х		Х		4 Sct			
Blood sample for companion diagnostic development		Х													nedule			Sample to be taken on Day -1 in treatment Period 1 only.
Genetics sample for CES genotyping and optional genetic research [E5]		Х													of Activ			Sample to be taken on Day -1 in treatment Period 1 only.
Urine sample for metabolite analysis [E4]			x	<==	=====	=====	=====					=====	===>		rities			Pre-dose sample, immediately prior to dosing participants will be instructed to void their bladder into a collection container. Following dosing participants will be instructed to collect all urine voided for a 0- 24 hour collection.

207546

	1																
								Tr	eatme	nt Peri	od 4						Notes
Procedure	Day -10	24-48h Day	D						Day 1						Day 2	Day 3	If participants only take part in treatment Period 4 they will undergo screening assessments prior to this treatment Period
	Day -10 (±3 days)	24-48h following Day -10 visit	Day -1	Pre-dose	0 h	15 mins	30 mins	1 h	2 h	3 h	4 h	6h	8 h	12 h	24 h	48 h	as detailed in Section 2.1.
General		1	1	 											1	1	
Admission to unit for in- patient stay			Х														
Discharge from Unit following in-patient stay																х	
Outpatient visit	x	x															For baseline blister induction and sampling; see Section 2.1.1.1 and Section 2.1.1.2. The baseline blister samples collected will be repeated if > 4 months elapses between the baseline blister and the challenge treatment Period (eg if a reserve in the study is not dosed and is subsequently rescreened for a later cohort).
Safety Assessments in	cludir	ng labora	tory te	ests											•		
Brief Physical Exam			Х													X	
Vital signs			х	Х	5	See Se	ction 2	.1.1.1 :				for vita lenges	al signs	s meas	urement	s in	BP, HR, temperature, respiratory rate.
Body weight			х														Body weight will be measured on Day -1 to calculate doses for challenges.
12-Lead ECGs			x	x					x		x		x	x	x	x	12 lead ECGs will be performed in triplicate at Day -1, pre- dose Day 1, Day 2 and Day 3. Single ECGs will be performed at other time points and if any cardiac symptoms are experienced. ECGs to be performed prior to any blood draws or dosing scheduled for the same nominal time point.

2.1.1. Part A Period 4 Schedule of Activities

CONFIDENTIAL

								Ti	reatme	ent Peri	iod 4						Notes
Procedure	Day -10 (±3 days	24-48h Day -	Day						Day 1						Day 2	Day 3	If participants only take part in treatment Period 4 they will undergo screening assessments prior to this treatment Period
	(±3 days)	24-48h following Day -10 visit	ay -1	Pre-dose	0 h	15 mins	30 mins	1 h	2 h	3 h	4 h	6h	8 h	12 h	24 h	48 h	as detailed in Section 2.1.
Telemetry				<==	<=====> From 1 h pre-dose to 24 h post-dose. For receiving the LPS-challenge, telemetry in a minimum of 12 hours post-LPS or untit no clinically significant findings for 4 hour longer).												
Haematology			X									Х			Х	Х	24 and 48 hour samples will be taken prior to participants receiving breakfast
Coagulation												Х			Х	Х	24 and 48 hour samples will be taken prior to participants receiving breakfast
Clinical Chemistry			х									Х			Х	Х	24 and 48 hour samples will be taken prior to participants receiving breakfast
Urinalysis			х									Х			Х	Х	24 and 48 hour samples will be taken prior to participants receiving breakfast
Drug / Alcohol Test			Х														
Urine Cotinine			Х														
Visual forearm check (including cosmetic assessment)	x		х	See	Sectior	n 2.1.1			n 2.1.1 to cha			forearn					
AE / SAE review			SA	Es collec	ted fro	m sign	ing of	inform		sent fo st dose		Es colle	cted c	m time			
Concomitant Medication Review					Mo	onitore	d from	first do	ose un	til the e	end of	the fina	ıl treatı	ment P	eriod		

CONFIDENTIAL

								Tı	reatme	ent Peri	od 4						Notes
Procedure	Day -10 (±3 days)	24-48h Day -	Da						Day 1						Day 2	Day 3	If participants only take part in treatment Period 4 they will undergo screening assessments prior to this treatment Period
	±3 days)	24-48h following Day -10 visit	Day -1	Pre-dose	0 h	15 mins	30 mins	1 h	2 h	3 h	4 h	6h	8 h	12 h	24 h	48 h	as detailed in Section 2.1.
Treatment / agent adm	inistra	ation and	d PK s	ampling	1	1				1	1		1			1	
Study Drug / Placebo Administration					Х												
In vivo LPS Challenge							<==		===>								LPS administration to be performed at GSK3358699 systemic C _{max} ; anticipated to be between 0.5-2hrs post GSK3358699 dose.
OR in vivo GM-CSF Challenge							<==				==>						GM-CSF administration to be performed at GSK3358699 systemic C _{max} ; GM-CSF will be administered as an infusion over 2 hours and the start of the infusion is anticipated to be between 0.5-2hrs post GSK3358699 dose.
Blood sampling for systemic PK [S1] and [S2]				х		х	х	X	X		х	Х	x	x	x	x	
Blood sampling for intracellular PK [S3]											Х				Х		
Cantharidin application and PD sampling						See	e Secti	on 2.1.	1.1 an	d Secti	on 2.1	.1.2			•		

207546

2.1.1.1. Part A Period 4 Detailed SoA for LPS Challenge and Biomarker Sampling

	Day -10	24-48 hours f Day -10	D							es belo K3358				Day 2	Day 3	Notes
Procedure	Day -10 $(\pm 3 \text{ days})$	urs following -10 visit	Day -1	Pre-dose	0 h	20 mins	1 h	2 h	Зh	4 h	6h	8 h	12 h	24 h	48 h	
LPS challenge administration					х											See Section 2.1.1 for timing of LPS administration in relation to GSK3358699 / placebo dose.
Visual forearm check (including blister healing and cosmetic assessment)	х		x	x										х	x	Pre-cantharidin check to be within three hours prior to cantharidin application.
Cantharidin application	Х					Х										Day – 10: to be applied in the morning. Day 1: to be applied 20 minutes post LPS challenge.
Intravenous hydration with normal Saline at a rate of 250 mL / hr				<==	=====	=====	=====:	=====	=====	=====	=====	:==>				From 4 hours prior to LPS challenge administration until 8 hours after LPS challenge administration.
Vital Signs			x	x	<==:								===>	x	x	BP, HR, temp, respiratory rate. Pre-dose vital signs to be taken pre-LPS challenge administration then post-LPS challenge as follows: every half hour for the first 4 hours, hourly until 12 hours, then 6- 8 hourly until discharge. Frequency can be increased if symptomatic.
Blood sample for circulating inflammatory biomarkers [E2a]				х			х	x		х	х			х	x	
Blood sample for cellular activation markers [E2b]				х			х				х			х		
Blood sample in TruCulture tube for inflammatory markers [E2c]				x							х					Pre-dose and 6 hours post LPS challenge: Null and LPS tubes at both time points.
Blood sample for gene panel [E2d]				х			х		х		х			х		
Blister sample for biomarkers, blister volume and cell counts [E3]		x												х		Sample to be taken approx 24-48 hours post blister induction (time point being defined as part of ongoing enabling study).

207546

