Participants who are enrolled in the dose escalation treatment Periods of Part A may choose to only take part in the dose escalation treatment Periods 1-3, or may choose to also take part in the challenge treatment period (Period 4). If a participant chooses to participate in the dose escalation treatment Periods 1-3 only, or does not (at screening) meet the eligibility criteria specific to challenges (treatment Period 4), a new participant will be recruited for treatment Period 4 only and will be regarded as a replacement subject.

During each treatment Period, participants in an individual cohort will be admitted to the clinical unit on Day -1 and will remain there until completion of all assessments on Day 3 (at approximately 48 hours post-dose).

Upon conclusion of the dose escalation phase of Part A, an additional dosing Period (treatment Period 4) will be included. Eligible participants in both cohorts will attend the clinic for outpatient visits on Day -10 (\pm 3 days) to have control blisters induced on the forearm (0.2% cantharidin) and will have a blister sample taken at approximately 48hrs post blister induction. Participants in Cohort 1 will be administered intravenous (IV) *in vivo* LPS challenge at a dose of 0.75 ng/kg following treatment with GSK3358699 or placebo and will then have blisters induced on the forearm (0.2% cantharidin). Similarly, participants in Cohort 2 will be administered 60 µg/m² IV *in vivo* GM-CSF challenge

following treatment with GSK3358699 or placebo and will then have blisters induced on the forearm (0.2% cantharidin).

Of the nine participants within each cohort, six will receive GSK3358699 and three will receive placebo in treatment Period 4, as per the randomisation schedule. The doses of LPS and GM-CSF to be administered to participants have been defined as part of an ongoing clinical enabling study (Study ID 207654) and will be administered around the time of the GSK3358699 systemic maximum concentration (C_{max}) defined from data gathered in treatment Periods 1-3. The dose levels of GSK3358699 administered to either cohort in Period 4 will be identical and will be decided by the dose escalation committee (DEC). This will be a single dose of GSK3358699 that is within the range investigated in treatment Periods 1-3 of Part A.

[figure not shown]
The duration of treatment Period 4 from Day -1 onwards and the implementation of sentinel dosing will be the same as for each of the treatment Periods 1-3.

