2.1.1.2. Part A Period 4 Detailed SoA for GM-CSF challenge and Biomarker Sampling

	Day -10	24-48 hou Day -	Da	Day 1	l - pre-d of				times b not GS					rt time	Day 2	Day 3	Notes
Procedure	Day -10 (± 3 days)	24-48 hours following Day -10 visit	Day -1	Pre-dose	0 h	1 h	2 h	2.3 h	3 h	4 h	5h	6 h	8 h	12 h	24 h	48 h	
GM-CSF challenge administration					<===		===>										See Section 2.1.1 for timing of the start of the GM-CSF infusion in relation to GSK3358699 / placebo dose. GM-CSF will be administered as an infusion over 2 hours.
Visual forearm check (including blister healing and cosmetic assessment)	х		х			Х									x	х	Pre-cantharidin check to be within three hours prior to cantharidin application.
Cantharidin application	х							х									Day – 10: to be applied in the morning. Day 1: 2 hours and 20 minutes after the start of the GM-CSF challenge.
Vital Signs			x	x	<===			=====		=====	=====		=====	:==>	x	x	BP, HR, temp, respiratory rate. Pre-dose vital signs to be taken pre-GM-CSF challenge administration then post-GM-CSF challenge as follows: every half hour for the first 4 hours, hourly until 8 hours, then 6- 8 hourly until discharge. Frequency can be increased if symptomatic.
Blood sample for circulating inflammatory biomarkers [E2a]				х			Х		x	x	x	x	х		x	х	
Blood sample for cellular activation markers [E2b]				х			Х		х		Х		Х		х		
Blood sample for gene panel [E2d]				Х					Х		Х		Х		Х		
Blister sample for biomarkers, blister volume and cell counts [E3]		x													x		Sample to be taken approx 24-48 hours post blister induction (time point being defined as part of ongoing enabling study).

	Scr					Tr	eatmen	t Period	ds 1 an	d 2					Follo	Notes
Procedure	Screening (up prior to [Da					Da	ay 1					Day 2	Day 3	Follow-up 1 (7-14 days last dose)	
	g (up to 35 Days r to Day 1)	Day -1	Pre-dose	0 h	15 mins	30 mins	1 h	2 h	4 h	6 h	8 h	12 h	24 h	48 h	14 days post- ose)	
General																
Informed consent	Х															
Inclusion and exclusion criteria	x	x														Day -1 assessment is to recheck eligibility against medical conditions, prior therapy etc, but not against Day -1 clinical chemistry and haematology results (see Section 9.4.7).
Demography	Х															
Medical/medication/drug/alcohol history	х	х														Includes substance usage and family history of premature CV disease and current medical conditions.
Admission to unit for in-patient stay		Х														
Discharge from Unit following in- patient stay														х		

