LPS challenge administration			х											See Section 2.4.1 for timing of LPS administration in relation to GSK3358699 / placebo dose.
Visual forearm check (including blister healing and cosmetic assessment)	х	х										х	х	Pre-cantharidin check to be within three hours prior to cantharidin application.
Cantharidin application				Х										To be applied 20 minutes post LPS challenge.
Intravenous hydration with normal Saline at a rate of 250 mL / hr		<==		=====				=====	=====	===>				From 4 hours prior to LPS challenge administration until 8 hours after LPS challenge administration.
Vital Signs	x	x	<==		=====						===>	x	x	BP, HR, temperature, respiratory rate. Pre-dose vital signs to be taken pre-LPS challenge administration then post-LPS challenge as follows: every half hour for the first 4 hours, hourly until 12 hours, then 6-8 hourly until discharge. Frequency can be increased if symptomatic.
Haematology	Х								Х		Х	Х	Х	
Coagulation	Х							Х						
Blood sample for circulating inflammatory biomarkers [E2a]		х			х	Х	Х		Х			Х	Х	
Blood sample for cellular activation markers [E2b]		х			х				х			х	х	
Blood sample for gene panel [E2d]		х			х		х		х			х		
Blister sample for biomarkers, blister volume and cell counts [E3]													х	Blisters harvested approx 48 h post cantharidin application.

2.4.3. Part C Day 14 Detailed SoA for GM-CSF Challenge and Biomarker Sampling Cohorts 4 and 8 (with challenges)

	Da	Day			and all GM-CS							start	Day 15	Day 16	Notes
Procedure	Day 13	Pre-dose	0 h	1 h	2 h	2h 20mins	3 h	4 h	5h	6 h	8 h	12 h	24 h	48 h	
GM-CSF challenge administration			<==		===>										See Section 2.4.1 for timing of the start of the GM-CSF infusion in relation to GSK3358699 / placebo dose. GM-CSF will be administered as an infusion over 2 hours.
Visual forearm check (including blister healing and cosmetic assessment)	x			х									x	х	Pre-cantharidin check to be within three hours prior to cantharidin application.
Cantharidin application						Х									2 hours and 20 minutes after the start of the GM-CSF challenge.
Vital Signs	x	х	<=:									==>	x	х	BP, HR, temperature, respiratory rate. Pre-dose vital signs to be taken pre-GM-CSF challenge administration then post-GM-CSF challenge as follows: every half hour for the first 4 hours, hourly until 8 hours, then 6-8 hourly until discharge. Frequency can be increased if symptomatic.
Haematology	Х							Х			Х		Х	Х	

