Further details of the DEC remit are provided in Section 12.3 and in the Dose Escalation Plan (DEP). This plan outlines how the study team will ensure data integrity used in dose selection decisions by performing clinical data review and appropriate quality control of data prior to making dose selection decisions, as well as outlining the responsibilities of the investigators and site staff for reporting safety data, participation during dose escalation meetings, and confirmation that the data used for dose escalation are accurate and complete.

Further information on dose decisions / modifications is provided in Section 7.2.

5.1.1.2. Part A LPS or GM-CSF challenge with cantharidin-induced blisters – Cohort 1 and Cohort 2:

Upon conclusion of the dose escalation phase of Part A, an additional dosing Period (treatment Period 4) will be included. Eligible participants in both cohorts will attend the clinic for outpatient visits, on Day -10 (\pm 3 days) to have control blisters induced on the

forearm (0.2% cantharidin), and will have a blister sample taken at approximately 48hrs post-blister induction. Participants in Cohort 1 will be administered an IV *in vivo* LPS challenge at a dose of 0.75 ng/kg following treatment with GSK3358699 or placebo and will then have blisters induced on the forearm (0.2% cantharidin) approximately 20 minutes after the challenge. Similarly, participants in Cohort 2 will be administered 60 μ g/m² *in vivo* GM-CSF challenge as an IV infusion following treatment with GSK3358699 or placebo and will then have blisters induced on the forearm (0.2% cantharidin) approximately 20 minutes after the challenge. Similarly, participants in Cohort 2 will be administered 60 μ g/m² *in vivo* GM-CSF challenge as an IV infusion following treatment with GSK3358699 or placebo and will then have blisters induced on the forearm (using 0.2% cantharidin) approximately 20 minutes after the end of the GM-CSF infusion. Of the nine participants within each cohort, six will receive GSK3358699 and three will receive placebo in treatment Period 4, as per the randomisation schedule.

The duration of treatment Period 4 from Day -1 onwards and the implementation of sentinel dosing will be the same as for each of treatment Periods 1-3. The dose levels of GSK3358699 administered to either cohort in treatment Period 4 will be identical and will be decided by the DEC.

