The doses of LPS and GM-CSF to be administered to participants have been defined as part of a clinical enabling study [GlaxoSmithKline Document Number 2016N309726_01 Study ID 207654] and will be administered at the GSK3358699 systemic C_{max} defined from data gathered in treatment Periods 1-3. The dose levels of GSK3358699 administered to either cohort in treatment Period 4 will be identical. This will be a single dose of GSK3358699 that is within the range investigated in treatment Periods 1-3 of Part A and the decision on the dose level will be made by the DEC based on all available safety, tolerability, PK and PD data from treatment Periods 1-3.

The *in vivo* challenges included in treatment Period 4 will act as a pre-determinant to their inclusion in Part C. That is, if GSK3358699 treatment does not robustly inhibit production of inflammatory mediators and leukocyte activation following either low dose *in vivo* LPS or GM-CSF challenges and blisters in Part A, the same challenge will not be investigated in Part C. Inclusion of challenges in Part C will be decided once all the data has been generated from treatment Period 4 in Part A, and the criteria will be specific for each challenge. Inclusion of the challenges in Part C will be based on inhibition of multiple inflammatory biomarkers which may include, but are not limited to, TNF, IL-6, MCP-1 and CRP for the LPS challenge, leukocyte activation markers, thymus and activation regulated chemokine (TARC) and Macrophage-Derived Chemokine (MDC) for the GM-CSF challenge, and leukocyte counts, interferon gamma-induced protein-10 (IP-10), MMP-9, transforming growth factor (TGF)- β and leukocyte activation markers for the cantharidin-induced blisters.

5.1.1.3. Part A Dose Escalation / Challenge Total Duration:

There will be a minimum of 14 days between each dosing in Cohort 1 and Cohort 2 to ensure that appropriate dose decisions can be made during the dose escalation phase. This results in a minimum 28 day washout Period between dosing in each treatment Period for a particular cohort (including between treatment Periods 3 and 4).

The total duration of this part of the study for each participant, including screening and follow-up, is approximately 19 weeks for participants taking part in all three dose escalation treatment Periods and 23 weeks if a participant takes part in all four treatment

[figure not shown]

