10.2. Sample Size Determination

10.2.1. Sample size assumptions

At each dose level studied in Part A there will be approximately nine participants; six randomised to each of the GSK3358699 treatment groups and three receiving placebo in any one period. In Part A, each participant will be randomised to one of three sequences for the dose escalation phase.

In Part B of the study there will be approximately six participants, all receiving GSK3358699 (randomised to either fed or fasted administration), each participant will be randomised to one of two sequences. In Part C approximately fourteen participants in Cohort 4 were planned (ten randomised to the GSK3358699 treatment group and four receiving placebo, in a 5:2 ratio). In Cohorts 5 - 7 approximately eighteen participants are planned (nine randomised to each of the GSK3358699 treatment groups and nine receiving placebo, in a 1:1 ratio) and in Cohort 8 approximately twenty subjects are planned (ten randomised to the GSK3358699 treatment group and ten receiving placebo, in a 1:1 ratio).

Refer to Section 7.2 for further information on sample size and randomisation changes in the event of any dose modifications.

The sample size is based on feasibility.

The primary objective of the study is safety, where the number of safety events would be of interest, for example the number of participants experiencing a particular adverse event. At each dose level in Part A six participants will receive GSK3358699. If 0/6 of a

particular safety event in the GSK3358699 group is observed, using a Bayesian approach to determine the credible interval around an observed safety event, we would assume a flat Beta (1,1) prior, and if we were to observe 1 safety event in 6 then the posterior distribution would be Beta (2, 6), where we can be 95% certain that the true probability of the safety event lies between 0.04 and 0.58.

Sample size sensitivity

A sample size sensitivity analysis has been conducted on the primary endpoint, to investigate different safety event rates. If the number of subjects who completed each active dose reduces, then the true incidence rates of safety events that could not be ruled out would change. These changes are outlined below:

N on GSK3358699 Completing Cohort	Number of a particular safety event observed with GSK3358699	Upper limit of exact 95%CI indicating that a true incidence rate of x% could not be ruled out
6	2	71%
6	3	82%
	0	46%
5	1	64%
	2	78%
	0	52%
4	1	72%
	2	85%

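### The Part A Period 4 blister harvest time conflicts between the protocol text (control blister at about 48 h) and the schedules (post-challenge blister on Day 2 / 24 h, note allowing 24 to 48 h)

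*Protocol*

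**What the plan says.** **Text, control blister.** The protocol synopsis says that participants "will have a blister sample taken at approximately 48hrs post blister induction". Section 5.1.1.2 agrees: "will have a blister sample taken at approximately 48hrs post-blister induction". Neither gives a harvest time for the blister raised after the LPS or GM-CSF challenge in Part A.

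**Part A schedules.** In Sections 2.1.1.1 and 2.1.1.2 the blister row [E3] has two marks. The control mark sits under a column headed "24-48 hours following Day -10 visit". The post-challenge mark sits under Day 2 / 24 h, and Day 3 / 48 h is blank. One note serves the whole row: "Sample to be taken approx 24-48 hours post blister induction (time point being defined as part of ongoing enabling study".

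**SAP.** Sections 13.1.1.2 and 13.1.1.3 carry the same marks and the same note. The SAP's narrative in Section 2.3 does not settle the point: it introduces a range but gives only about 48 h.

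**Part C.** Section 2.4 states "Blisters harvested approx 48 h post cantharidin application", with the mark on Day 16. Sections 2.4.2 and 2.4.3 agree.

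**Use of the data.** Section 5.1.1.2 says: "The *in vivo* challenges included in treatment Period 4 will act as a pre-determinant to their inclusion in Part C". It lists blister leukocyte counts, soluble mediators and activation markers among the inputs, beside separate blood markers for each challenge.

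**The concern.** Harvest time is an operative sampling instruction, and here the text and the tables do not give the same one. A unit that takes the control time from the text and the post-challenge time from the table mark would collect two blisters of very different age from one participant.

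Sections 2.1.1 and 9.8.2 call the Day -10 sample a baseline and have it repeated if more than 4 months pass, so it is plainly meant as a within-participant reference. If the two blisters differ in age, a change from that baseline mixes the effect of challenge and drug with the effect of blister age. E3 covers blister volume, cell counts and mediators, all read from that fluid. Part A results at one age would also not line up with Part C results at another. If harvest times varied within 24 to 48 h, that would add noise to groups of 6 active and 3 placebo per challenge.

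**Working it through.** No power or alpha figure is involved (Section 10.2.1: "The sample size is based on feasibility"), so the check is of times and of what an age difference does to each comparison.

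**Inputs**
- Cantharidin goes on 20 min (0.33 h) after LPS (2.1.1.1), or 2 h 20 min (2.33 h) after the start of GM-CSF (2.1.1.2).
- Post-challenge harvest mark: the 24 h column. I assume that it is timed from the challenge, as the Day 1 columns of these tables are.
- Control age: 48 h (text), or 24 to 48 h (schedule).

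**Blister age** = column time − cantharidin time; **gap** = control age − blister age.

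| Challenge | Age at 24 h mark | Gap vs 48 h control | Gap vs 24 h control |
|---|---|---|---|
| LPS | 24 − 0.33 = 23.67 h | 24.33 h | 0.33 h |
| GM-CSF | 24 − 2.33 = 21.67 h | 26.33 h | 2.33 h |

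The gap is large only if the control time comes from the text and the post-challenge time from the table. Were the mark in the 48 h column, the ages would be 47.67 h and 45.67 h, which is 0.33 h and 2.33 h short of a 48 h control.

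**Effect on the comparisons.** Take an additive log-scale model with assumed values, since the documents give none: challenge effect 0.8, drug effect −0.5, and a shift *a* due to the age difference, shared by both arms. Placebo change = 0.8 + *a*; active change = 0.8 + *a* − 0.5.

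| *a* | Placebo change | Active change | Active − placebo |
|---|---|---|---|
| 0 | 0.8 | 0.3 | −0.5 |
| 0.3 | 1.1 | 0.6 | −0.5 |
| 0.7 | 1.5 | 1.0 | −0.5 |
| 1.0 | 1.8 | 1.3 | −0.5 |

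The change from control moves one for one with *a*, while the randomised contrast does not move. The direction of *a* is unknown: a negative value would make an active-only change look like inhibition, and a positive one would hide it. If the drug effect itself varies with blister age, the contrast is valid for the age harvested but need not carry over to blisters of another age.

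**Covariate adjustment.** If every control is 48 h old and every post-challenge blister has the age above, age = 48 − 24.33 × status (LPS) or 48 − 26.33 × status (GM-CSF), where status is 0 for control and 1 for post-challenge. Within each challenge, age is then an exact linear function of status. A model cannot separate the two, and restricting to equal ages leaves no pairs.

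**The case against.** The best defence is that no single passage prescribes a 24 h versus 48 h comparison. Within the schedules both samples share one open 24 to 48 h window, and a control taken at the 24 h end would be only 0.33 h or 2.33 h older than the post-challenge blister. The note also looks like a leftover. It calls the enabling study ongoing, while the amendment summary records the harvest time as confirmed after that study ended. The protocol's LPS table still carries the E2c row, whose section was deleted. Section 2 allows timings to change with documented approval and no amendment, so the time actually used may be in study files not available here. All of this stands, and it means that the mismatch is a literal reading and not an established fact. It does not remove the conflict: the SAP dropped the E2c row from its copy of the LPS table but kept the blister mark and note.

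A reader might go further and infer that the evidence deciding whether challenges enter Part C is confounded with time. The documents do not support that. The decision concerns inhibition by GSK3358699. Period 4 has a randomised concurrent placebo group (6:3 per cohort) on the same schedule, Section 5.4 names placebo as the control for PD assessments, and blister markers are only part of the evidence. A reader might also infer drift between sites, but the study is run in one clinical unit.

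**Conclusion.** The inconsistency is real and stands in the current text of the protocol and the SAP. Read literally, it makes post-challenge blisters about 24 to 26 h younger than the baseline blister for all 18 planned Period 4 participants (12 active, 6 placebo). That would bias a baseline-to-post-challenge change for E3 and make Part A and Part C blisters not comparable.

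The active-versus-placebo contrast is protected as long as the age effect is additive and common to both arms. The decision on Part C challenges is exposed only if the drug effect depends on blister age, or if change from control is read without placebo. No document says which comparison was to be used.

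The practical reach is limited. E3 is exploratory and reported outside the SAP (Section 11), and dosing in Part C stopped within Cohorts 4 and 5, so the planned Cohort 8 challenges were not given. It still matters for any blister analysis run separately, which SAP Sections 2.1 and 3.1 leave open.

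**What to change.** - Reconcile protocol Sections 2.1.1.1 and 2.1.1.2, and SAP Sections 13.1.1.2 and 13.1.1.3, with the synopsis, Section 5.1.1.2 and the Part C schedules. Control and post-challenge blisters should have one stated harvest time, counted from cantharidin application. Which time applies is for the sponsor to state.
- Replace the open note with that time, and align the 24 to 48 h column headings over the control sample, including the one in Section 2.4.
- Check the result against the Day 3 discharge. As an example, 48 h after cantharidin falls 48.83 to 50.33 h (LPS) or 50.83 to 52.33 h (GM-CSF) after the study dose, using the anticipated challenge start 0.5 to 2 h after dosing.
- Record actual hours from cantharidin to harvest for every blister and report them with any E3 result.
- State that E3 conclusions, and any decision based on Period 4 blisters, rest on concurrent active versus placebo at matching blister age.
- Do not rely on a blister-age covariate to rescue a control-versus-treated comparison.

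The cost is wording in four tables, one derived time per blister, and one sentence in whatever plan governs the exploratory analysis.
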